All abaloparatide-SC doses are to be given in the periumbilical region, rotating the site of injection each day. All abaloparatide-sMTS doses are to be applied on the thigh for 5 minutes. If it is deemed medically necessary for the study drug to be administered at an anatomic site other than what is required per protocol, the alternate site of study drug application/injection is to be recorded and the reason for change documented in the medical chart in the source documents as a protocol deviation.

Subjects will be dispensed abaloparatide-SC pens each month and will be instructed to use a new abaloparatide-SC injection pen after each 30-day period. A new set of abaloparatide-sMTS patches will be provided after each 30-day period. At each study site visit during the Treatment Period, the used and unused abaloparatide-SC injection pens and sMTS patches should be returned. All returned study drug should either be destroyed at the study site following that site's local procedures or sent to a depot identified by the Sponsor.

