    - Note: If the measurement of drug remaining in any used pen is missing, then 100% compliance will be assumed for the intended treatment period for which the pen with missing measurement of drug remaining was dispensed. For each pen dispensed prior to Month 11 visit, the intended treatment period is a 30-day period starting from the day when first dose was taken from the pen. For the pen dispensed at Month 11 visit, the intended treatment period is a period less than or equal to 30 days starting from the day when first dose was taken from the pen to the EOT day. The number of doses taken from the pen with missing measurement of drug remaining is a value less than or equal to 30, which will be based on the number of doses taken from the pen(s) with non-missing measurement of drug remaining and the duration of the treatment period. The number of doses delivered would be the minimum of the following:
      - Total doses taken from pens with non-missing measurements of drug remaining (calculated as:  $[45.5 \text{ mm} \times \text{Number of pens with non-missing measurements of drug remaining} - \text{Sum of measurements of drug remaining from all pens with non-missing measurements of drug remaining}] / 1.08 \text{ mm}$ ) +  $30 \times \text{number of pens with missing measurement of drug remaining}$
      - Overall duration of study drug exposure (last dose date - first dose date + 1)
    - Percent compliance (%) to study drug administration =  $(\text{Number of doses delivered} / \text{Overall duration of study drug exposure}) \times 100\%$

For the abaloparatide-sMTS group, the total number of doses delivered and study drug compliance will be calculated in two ways as follows:

- **Based on missed doses in subject diary:**
  - Number of doses delivered = Overall duration of study drug exposure - Total number of missed doses per subject diary
  - Percent compliance (%) to study drug administration =  $(\text{Number of doses delivered} / \text{Overall duration of study drug exposure}) \times 100\%$
- **Based on number of patches returned:**
  - Number of doses delivered =  $20 \times \text{Number of kits dispensed} - \text{Sum of patches returned in all dispensed kits}$ . The number of patches dispensed per kit is 20.

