- Note: If the number of patches returned in any dispensed kit is missing, then 100% compliance will be assumed for the treatment period for which the unreturned kit was dispensed. The number of patches used from the unreturned kit is a value less than or equal to 20, which will be based on the number of patches used from the returned kit(s) dispensed at the same visit as the unreturned kit. The number of doses delivered would be the minimum of the following:
  - Total patches taken from kits with non-missing number of patches returned (calculated as:  $20 \times \text{Number of non-missing kits} - \text{Sum of number of patches returned from all non-missing kits}$ )  $+ 20 \times \text{number of kits with missing number of patches returned}$
  - Overall duration of study drug exposure (last dose date - first dose date + 1)
- Percent compliance (%) to study drug administration =  $(\text{Number of doses delivered} / \text{Overall duration of study drug exposure}) \times 100\%$

The duration of study drug exposure, duration category in months ( $\leq 1$  month,  $1 < \text{to } \leq 3$  months,  $3 \text{ to } \leq 6$  months,  $6 \text{ to } \leq 9$  months, and  $> 9$  months), number of doses delivered, and percent compliance to study drug administration will be summarized by treatment group for the Safety, mITT and PP populations. The summaries will not be provided for the ITT population since the Safety and ITT populations represent the same subjects with respect to study drug exposure.

The study drug exposure and compliance will also be summarized by region (North America and Europe) for the Safety, mITT and PP populations.

To evaluate the relationship between study drug exposure and the antibody status, the duration of study drug exposure and percent compliance to study drug administration will also be summarized by antibody status (ADA-, ADA+/Nab+, ADA+/Nab-, All ADA+, and Overall) using the Antibody Population.

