Two different patches will be dispensed to subjects in the abaloparatide-sMTS group. The ultra-low bioburden patches will be dispensed from Day 1 to all subjects. Sterile patches (the patches intended for commercial use) will be dispensed to subjects after confirmation that the sterile product is bioequivalent to the ultra-low bioburden product (Study 058-05-023). For the abaloparatide-sMTS group, the duration of study drug exposure, duration category in months, number of doses delivered and percent compliance with study drug administration using two calculations of percent compliance will also be summarized by patch type (ultra-low bioburden, sterile) for the Safety, mITT and PP populations.

If a subject is shown to be  $<80\%$  compliant with study drug administration using both calculations of study drug administration compliance for abaloparatide-sMTS group, or is  $<80\%$  compliant with study drug administration using both calculations of study drug administration compliance for the abaloparatide-SC group, this subject will be considered as having a critical protocol deviation and thus excluded from the PP Population.

Subjects' drug exposure and compliance will be carefully reviewed against the onset of the COVID-19 pandemic. Each subject's study drug exposure and compliance prior to 01 March 2020 and on or after 01 March 2020 will be calculated based on information collected from the subject diary:

- For subjects with last dose date prior to 01 March 2020 and subjects with first dose date on or after 01 March 2020, their duration of study drug exposure (days), number of doses delivered, and percent compliance to study drug administration relative to 01 March 2020 will be calculated as above based on the missed doses in subject diary
- For subjects who started taking the study drug prior to 01 March 2020 and continued on or after 01 March 2020, their duration of study drug exposure and compliance before 01 March 2020 and on or after 01 March 2020 will be calculated as follow:
  - Durations of study drug exposure relative to 01 March 2020:
    - Duration before 01 March 2020 = 29 February 2020 – date of first dose + 1
    - Duration on or after 01 March 2020 = Overall duration of study drug exposure – duration before 01 March 2020; where overall duration of study drug exposure = last dose date – first dose date + 1

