  - The numbers of doses delivered relative to 01 March 2020 (The number of doses provided to a subject is different at each visit between the abaloparatide-SC group and abaloparatide-sMTS group. Therefore, different formulas are used to calculate the number of doses delivered before 01 March 2020 for the two treatment groups):
    - Number of doses delivered before 01 March 2020 (abaloparatide-SC group) =  $A - (B + [C \times \min \{1, D / E\}])$ , and will be rounded to the nearest integer; where:
      - A = Duration of study drug exposure before 01 March 2020
      - B = Total number of missed doses from pens dispensed before 01 March 2020 and with scheduled return date before or on 01 March 2020
      - C = Number of missed doses from pens dispensed before 01 March 2020 but with scheduled return date after 01 March 2020
      - D = 01 March 2020 – last drug dispensing date prior to 01 March 2020
      - E = First drug dispensing date on or after 01 March 2020 – last drug dispensing date prior to 01 March 2020
    - Note: if there is no drug dispense on or after 01 March 2020, then E = Last dose date - last drug dispensing date prior to 01 March 2020
  - Number of doses delivered before 01 March 2020 (abaloparatide- sMTS group) =  $A - (B + C \times D)$ , and will be rounded to the nearest integer; where:
    - A = Duration of study drug exposure before 01 March 2020
    - B = Total number of missed doses from kits dispensed before 01 March 2020 and with scheduled return date before or on 01 March 2020
    - C = Number of missed doses from kits dispensed during the last drug dispensing visit before 01 March 2020 but with scheduled return date after 01 March 2020
    - D =  $(01 \text{ March 2020} - \text{last drug dispensing date prior to 01 March 2020})/30$
  - Number of doses delivered on or after 01 March 2020 = Number of doses delivered during whole study – number of doses delivered before 01 March 2020.
- The percent compliance (%) to study drug administration relative to 01 March 2020:

- Percent compliance before 01 March 2020 = (Number of doses delivered before 01 March 2020 / Duration of study drug exposure before 01 March 2020) × 100%
- Percent compliance on or after 01 March 2020 = (Number of doses delivered on or after 01 March 2020 / Duration of study drug exposure on or after 01 March 2020) × 100%.

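### SAP 4.3.1 contradicts itself on unreturned patch kits: the formula's flat 20 per missing kit can credit a 30-day period with up to 40 doses and can, in uncommon cases, change Per-Protocol membership

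*SAP*

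**What the plan says.** SAP 4.3.1 computes patch compliance in two ways, from missed doses in the diary and from patches returned. On kits it says "The number of patches dispensed per kit is 20". Where a kit's return count is missing, a note gives three instructions:

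- Full compliance is assumed: "then 100% compliance will be assumed for the treatment period for which the unreturned kit was dispensed".
- The missing kit's count may not exceed 20.
- That count is one "which will be based on the number of patches used from the returned kit(s) dispensed at the same visit as the unreturned kit".

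The formula that follows defines doses delivered as the smaller of two totals. The first is the patches used from kits with known returns plus 20 times the "number of kits with missing number of patches returned". The second is the overall duration of exposure in days.

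For pens, the parallel note says "The number of doses taken from the pen with missing measurement of drug remaining is a value less than or equal to 30", and the formula adds 30 per pen with a missing reading. The period for the pen dispensed at Month 11 may be shorter than 30 days.

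A patch subject leaves PP for compliance only when below 80% "using both calculations of study drug administration compliance for abaloparatide-sMTS group". SAP 4.4.1.2 repeats the primary model in PP as support for the mITT result.

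**The concern.** The note and the formula give different counts for the same kit. The formula ignores the companion kit, and its only limit applies to the whole study, so one period can be credited with more daily doses than it has days. The surplus does not stay in that period. It makes up for doses missed elsewhere, until the total reaches the exposure duration.

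Because both figures must fail before a subject is excluded, an inflated return figure overrides a failing diary. PP is meant to describe women who took the drug, and the 80% criterion should not be met by doses that could not have been taken. Two programmers working from this text could also build different PP sets.

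**Working it through.** The SAP gives no worked compliance figure, so there is none to reproduce. I applied its rules directly.

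**Inputs**
- 20 patches per kit, and the missing-kit note and formula: SAP 4.3.1.
- Resupply: Protocol 5.6 says "A new set of abaloparatide-sMTS patches will be provided after each 30-day period".
- Kits per period: two, by inference. One kit of 20 cannot cover 30 daily doses, and the note refers to other kits from the same visit. SAP 4.3.1 also says "The number of doses provided to a subject is different at each visit between the abaloparatide-SC group and abaloparatide-sMTS group".
- PP exclusion: both figures below 80% (SAP 4.3.1), or exposure under 90 days (Appendix B, B1).
- Missed doses: up to 28 cumulative days without withdrawal, and suspensions of up to 14 continuous days (Protocol 4.7).

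**Credit for one 30-day period.** Let k be the patches used from the returned companion kit.
- Formula: k + 20.
- Note: k + min(20, 30 − k).

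| k | Formula | Note |
|---|---|---|
| 0 | 20 | 20 |
| 5 | 25 | 25 |
| 10 | 30 | 30 |
| 15 | 35 | 30 |
| 20 | 40 | 30 |
| both kits missing | 40 | 30 |

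The two differ only when k exceeds 10 or both kits are missing. The excess is at most 10 doses per full period.

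**Example A: within the 28-day allowance, misses spread evenly.** Exposure is 90 days and patches used are 20, 21 and 21, so 28 are missed.
- Diary: 62/90 = 68.9%.
- The second kit of one 21-patch period is missing and its companion came back empty.
- Formula: 20 + 21 + 40 = 81, and 81/90 = 90.0%. Kept in PP.
- Note: 20 + 21 + 30 = 71, and 71/90 = 78.9%. Excluded.

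**Example B: within the allowance, misses clustered.** Exposure is 120 days and patches used are 30, 30, 16 and 16 (two 14-day gaps).
- Diary: 92/120 = 76.7%.
- The second kit of a fully dosed period is missing and its companion came back empty.
- Formula: 92 + 10 = 102, and 102/120 = 85.0%. Kept.
- Note: 92/120 = 76.7%. Excluded.

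More generally, take exposure D with 28 doses missed in other periods. The formula gives D − 18 and the note D − 28. The formula keeps the subject if D − 18 ≥ 0.8D, that is D ≥ 90. The note excludes her if D − 28 < 0.8D, that is D < 140.

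**Example C: outside the allowance.** Exposure is 360 days with 21 patches used in each of 12 periods, so 108 doses are missed.
- Diary: 252/360 = 70.0%.
- Second kits missing in two periods. Formula: 252 − 42 + 80 = 290, or 80.6%, kept. Note: 252 − 42 + 60 = 270, or 75.0%, excluded.
- Under the note, four missing kits are needed to reach 288/360 = 80.0%.

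**The case against.** **Such subjects should be few.** With at most 28 missed doses, the diary falls below 80% only if exposure is under 28/0.2 = 140 days, and B1 already removes exposure under 90 days. If use is even over time, one missing period credited at 30, as the note intends, gives D − 28 + 840/D doses. That reaches 80% of D from 97 days on. With 27 missed it does so already at 90 days (63 + 9 = 72). Under even use the surplus therefore decides membership only at 28 missed and about 90 to 96 days. This stands, with two limits. Example B shows that clustered misses widen the range to 90–139 days, and SAP 4.3.1 tabulates more than 28 missed or interrupted days, so breaches are foreseen.

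**The contradiction is not the only cause.** The assumed 100% together with the both-calculations rule also keeps failing diaries in PP. With 21 patches used in each of three periods (diary 63/90 = 70.0%) and one second kit missing, the note alone gives 72/90 = 80.0%. This stands. A period cap reduces such retention but does not remove it.

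**The whole-study cap prevents absurd totals.** It keeps compliance at or below 100%, and formula and note agree when every other period is fully dosed. It does nothing for a subject who missed doses elsewhere, which is the case that matters here.

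**The programming specification may settle it.** SAP 2.2 requires a Per-Protocol Memo with a programming specification, final before database lock. It is not among the documents, so it may resolve the mismatch. The SAP text should still agree with itself.

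**A reader might infer bias between arms or towards non-inferiority.** The documents do not support that. Pen readings have their own weakness: Protocol 5.4.2 requires priming, and the SAP converts all plunger travel to doses with no deduction for it. Keeping under-dosed patch users in PP would, if under-dosing reduces BMD gain, work against the patch.

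**Conclusion.** The contradiction is plain on the page, and following the formula can produce an impossible dose count for a period. The excess is up to 10 doses per full 30-day period, enough for one missing kit to change PP membership (90.0% against 78.9% in Example A). This rests on two kits per period, which is inferred, and on reading the note as the smaller of 20 and the days not covered by the companion kit.

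The consequence is small. Only the supportive PP analysis and the compliance summaries (Safety, mITT and PP) are touched, and the primary mITT test is not. The number of subjects affected cannot be found from the documents and should be low. A reader might conclude that many non-adherent subjects will be kept, or that the PP estimate will move. Neither is shown. Severity: minor.

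**What to change.** In SAP 4.3.1, compute the missing-kit credit per dispensing period, as the note intends:

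credit = min(20 × missing kits, days in the period − patches used from the returned kit(s) of that visit)

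Then sum over periods and keep the existing cap at overall exposure. A period with a missing return is then never credited with more doses than it has days. State the number of kits dispensed per visit.

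Apply the same cap to the missing-pen rule: credit the smaller of 30 and the days in that pen's intended period. This matters for the Month 11 pen, where a flat 30 can exceed the period.

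Carry both rules into the Per-Protocol Memo specification before database lock. The cost is a few sentences, a small program change and possibly a slightly smaller PP set.

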## **2. SUBJECT ANALYSIS POPULATIONS**

### **2.1. Population Definitions**

Five subject populations will be considered in the statistical analyses of this study.

- Intention-to-Treat (ITT) population**

The ITT population consists of all subjects randomized into this study.

- Modified Intention-to-Treat (mITT) population**

The mITT population includes all randomized subjects who received at least one dose of study drug and had a baseline lumbar spine BMD measurement and at least one post-baseline lumbar spine BMD measurement.

- Safety population**

The Safety population consists of all randomized subjects who received at least one dose of study drug.

- Per-Protocol (PP) population**

The PP population consists of all mITT subjects who did not have any critical protocol deviations (described in [Section 2.2](#)).

- Antibody Population**

The Antibody population will include subjects in the Safety population who have at least one post-baseline anti-drug antibody assessment.

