### **3.9. Anti-Abaloparatide Antibody Status**

At Day 1, Day 14, Month 1, Month 3, Month 6, Month 9, Month 12/EOT, and Month 13/EOS, the anti-abaloparatide antibody (ADA) assessment in the serum samples for immunogenicity testing will be categorized by two outcomes:

- Negative for the ADA (ADA-)
- Positive for the ADA (ADA+)

For those subjects with a positive ADA (i.e., ADA is present), the serum samples will be further assessed for the presence of neutralizing anti-abaloparatide antibodies (NAb), and the results will be categorized by two outcomes:

- Negative for the NAb (NAb-)
- Positive for the NAb (NAb+)

Subject ADA status and presence of NAb by Month 12 (ADA-, ADA+/NAb+, ADA+/NAb-, All ADA+) will be defined as follows:

- Subjects will be classified as ADA- if they were ADA- in all post-baseline immunogenicity assessments during the 12-month treatment period.
- Subjects will be classified as ADA+ and NAb+ if they were ADA+ at any post-baseline immunogenicity assessment and NAb+ at any subsequent tests during the 12-month treatment period.
- Subjects will be classified as ADA+ and NAb- if they were ADA+ at any post-baseline immunogenicity assessment and NAb- at all subsequent tests during the 12-month treatment period.

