### **4.3. Exposure to Study Drug**

#### **4.3.1. Extent of Exposure and Treatment Compliance**

Subjects were trained by study personnel on how to self-administer study drug with the abaloparatide-SC injection pen or the abaloparatide-sMTS patch. On the days of study site visits, study drug must be administered at the study site to accommodate pre-administration and post-administration procedures.

The overall duration of study drug exposure will be calculated using the data recorded on the eCRF as follows:

- Overall duration of study drug exposure (days) = (date of last dose – date of first dose) + 1.

If the date of last dose is missing, then the earlier of the following 2 dates will be used as the last dose date for analysis and summary purposes: the final visit/early termination visit date or the last drug dispense date + 30 days.

For the abaloparatide-SC group, the total number of doses delivered and study drug administration compliance will be calculated in two ways as follows:

- **Based on missed doses in subject diary:**
  - Number of doses delivered = Overall duration of study drug exposure – Total number of missed doses per subject diary
  - Percent compliance (%) to study drug administration =  $(\text{Number of doses delivered} / \text{Overall duration of study drug exposure}) \times 100\%$
- **Based on measurement of drug remaining in pen:**
  - Number of doses delivered =  $[(45.5 \text{ mm} \times \text{Number of used pens}) - \text{Sum of measurements of drug remaining in all used pens}] / 1.08 \text{ mm}$ . Here the 45.5mm is the initial measurement of unused study drug in an unused injection pen and 1.08mm is the distance the plunger travels for each 80 ug dose from the pen.

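### Exposure duration by antibody status (SAP 4.3.1) tends to look longer in ADA+ women because status is decided over the same follow-up whose length is compared

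*SAP*

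**What the plan says.** SAP 4.3.1 states the aim and the layout. The aim: "To evaluate the relationship between study drug exposure and the antibody status, the duration of study drug exposure and percent compliance" are to be tabulated. The layout: "summarized by antibody status (ADA-, ADA+/Nab+, ADA+/Nab-, All ADA+, and Overall) using the Antibody Population". Duration covers the whole treatment course: "Overall duration of study drug exposure (days) = (date of last dose" minus date of first dose) + 1.

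SAP 3.9 fixes the groups over that same course. For the negatives: "Subjects will be classified as ADA- if they were ADA- in all post-baseline immunogenicity assessments during the 12-month treatment period". A woman is ADA+ if any post-baseline assessment is positive; for the neutralising subgroup, "if they were ADA+ at any post-baseline immunogenicity assessment and NAb+ at any subsequent tests during the 12-month treatment period". The schedule is: "At Day 1, Day 14, Month 1, Month 3, Month 6, Month 9, Month 12/EOT, and Month 13/EOS, the anti-abaloparatide antibody (ADA) assessment". A completer therefore gives six post-baseline samples on treatment (Day 14 and Months 1, 3, 6, 9 and 12).

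SAP 2.1 sets the entry rule: "The Antibody population will include subjects in the Safety population who have at least one post-baseline anti-drug antibody assessment".

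Neither SAP 3.9 nor SAP 4.3.1 mentions a landmark, a time-dependent antibody status or a restriction to completers.

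**The concern.** The grouping variable is settled during the interval whose length is then compared across the groups. A woman who stops soon after Day 14 with negative samples counts as ADA-, beside a completer with six negatives. Had the first woman stayed on treatment, she might have become ADA+. Early leavers therefore collect in the ADA- column and completers in the ADA+ column, whatever antibodies do. This is guarantee-time (immortal-time) bias.

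At stake is how the immunogenicity results are read. The duration rows can suggest that antibody-positive women stay on treatment longer when there is no link. They can also hide a real tendency for antibody-positive women to stop early, because the bias runs the other way.

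**Working it through.** The plan gives no figure for this table, so there is nothing to reproduce.

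**Direction.** Let D be exposure duration, and suppose D is independent of the antibody process. The chance of ever testing positive cannot fall as D rises, so mean D among ADA+ women is at least mean D among ADA- women. They are equal only if nobody stops early or if all positivity is detected at the first post-baseline sample.

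**Size under one set of assumptions.** From the documents: samples at Days 14, 30, 90, 180, 270 and 360, the any-positive rule, and at least one sample for entry. Assumed, because the documents do not give them: 50% seroconversion by 12 months at a constant hazard; 20% dropout, uniform over 360 days and unrelated to antibodies; scheduled samples only. The 10% in SAP 3.1 concerns women without a usable pair of lumbar spine BMD measurements, not discontinuation.

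A woman whose last sample is at day s is all-negative with probability 0.5^(s/360).

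| Stops (days) | Last sample s | Weight | Mean D | P(all negative) | ADA- weight | ADA+ weight |
|---|---|---|---|---|---|---|
| 14–30 | 14 | 0.2×16/360 = 0.0089 | 22 | 0.9734 | 0.0087 | 0.0002 |
| 30–90 | 30 | 0.2×60/360 = 0.0333 | 60 | 0.9439 | 0.0315 | 0.0019 |
| 90–180 | 90 | 0.0500 | 135 | 0.8409 | 0.0420 | 0.0080 |
| 180–270 | 180 | 0.0500 | 225 | 0.7071 | 0.0354 | 0.0146 |
| 270–360 | 270 | 0.0500 | 315 | 0.5946 | 0.0297 | 0.0203 |
| Completes | 360 | 0.8000 | 360 | 0.5000 | 0.4000 | 0.4000 |
| Total | | 0.9922 | | | 0.5472 | 0.4450 |

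Women who stop before Day 14 give no sample and are not in the table.

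- Mean exposure, ADA-: 169.07 / 0.5472 = 309 days.
- Mean exposure, ADA+: 154.87 / 0.4450 = 348 days.
- Gap: 39 days, with no true link to stopping.
- Share stopping early: ADA+ 0.0450 / 0.4450 = 10%; ADA- 0.1472 / 0.5472 = 27%.

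**Sensitivity (simulation, still 50% ADA and 20% dropout).**

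| Seroconversion timing | Samples | Gap (days) |
|---|---|---|
| Constant hazard | scheduled only | 39 |
| Constant hazard | plus EOT and EOS samples from every early leaver | 32 |
| Median 30 days | scheduled only | 15 |
| Median 30 days | plus EOT and EOS samples from every early leaver | 7 |
| All by Day 14, persistent | scheduled only | about 0 |

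**Masking.** Suppose seroconversion truly doubles the hazard of stopping (assumed; constant seroconversion hazard, 50% ADA, 20% baseline dropout). The planned comparison still shows ADA+ women treated about 32 days longer. A Month 3 landmark shows them about 16 days shorter, which is the true direction. Earlier conversion would weaken the masking.

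**Landmark under no link.** Status from samples up to Month 3, in women still on drug at that visit, with exposure counted afterwards, gives a gap within about 0.3 day.

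**Compliance.** Percent compliance divides doses delivered by the woman's own duration (SAP 4.3.1), so a longer stay does not raise it by this mechanism.

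**The case against.** - **The stated question has no direction.** Longer dosing giving more antibody detection is itself a relationship between exposure and status. The table also shows how far exposure differs between the antibody columns used for TEAEs (SAP 4.6.1) and AESIs (SAP 4.6.2), which a reader of those tables needs. This stands, and is why the table should be kept as description. But mean exposure grouped by whole-period status cannot separate that detection effect from any effect of antibodies on stopping.
- **Early leavers may be sampled more than once.** A reader might infer that a woman who leaves after Day 14 has one chance to test positive. Protocol 4.3.2 encourages withdrawn women to complete the EOT visit and return one month later, and ADA is drawn at both (Protocol 6.5.3). She may have up to three samples, although SAP 3.9 leaves open whether a follow-up sample counts. This narrows the gap from 39 to 32 days if all attend; it does not remove it.
- **Timing decides the size.** A reader might take a range such as 16 to 121 days (ADA 30 to 90%, dropout 10 to 30%) as the likely bias. That range fixes a constant hazard. The gap can be a few days or nil if conversion is early. This stands.
- **The arms may not be pooled.** The antibody sentence in SAP 4.3.1 lists no treatment split, so a reader might infer pooling. SAP 3.2 sets a by-treatment-group default. The text is ambiguous and does not establish pooling.
- **Low consequence.** The summary has no test, interval or decision rule, and antibody results are reported separately. This stands and limits the severity.

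**Conclusion.** The point holds for the duration rows. As specified, they tend to favour longer exposure in ADA+ women when antibodies have no effect on stopping, and they can mask antibody-related early stopping. With 50% ADA and 20% dropout assumed, the false gap is about 39 days under a constant hazard on scheduled samples, 32 with EOT and EOS samples from all early leavers, 7 to 15 with median conversion at 30 days, and about 0 if all conversion is detected at Day 14. The direction follows from the definitions; the size cannot be fixed from the documents.

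Two stronger readings are not supported. The compliance rows are not inflated by this mechanism. The non-inferiority conclusion is untouched, because the primary analysis compares randomised groups and does not use antibody status. Severity is minor.

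**What to change.** In SAP 4.3.1:

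1. Keep the whole-period table, labelled as a description of the antibody groups and not as an evaluation of the relationship.
2. For the stated purpose, add a landmark summary: ADA/NAb status from samples up to Month 3, in women still on study drug at that visit, with exposure duration counted after it. Repeat at Month 6.
3. State that results are shown by treatment group within antibody status.

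The cost is one SAP paragraph and one additional table on data already collected. The downside is that women who stop before the landmark are not in the comparison, and more are lost at Month 6 than at Month 3. Any early antibody-related stopping would have to be read from the by-visit ADA results already planned in SAP 4.6.3.

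### The 1 March 2020 compliance split prorates missed doses by the actual interval for SC but by a fixed 30 days for sMTS, so identical off-schedule data can give different or impossible values

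*SAP*

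**What the plan says.** SAP 4.3.1 computes exposure and compliance separately before and from 1 March 2020, and states that these "will be calculated based on information collected from the subject diary". For subjects on treatment across the date, doses delivered before it are the days of exposure before it (A), less missed doses from supplies due back by then (B), less a share of the missed doses (C) from the supply period that spans the date.

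- **SC:** the share is min{1, D/E}. D is the number of days from the last earlier dispensing to 1 March, and "E = First drug dispensing date on or after 01 March 2020 – last drug dispensing date prior to 01 March 2020". A note covers subjects who stop: "if there is no drug dispense on or after 01 March 2020, then E = Last dose date" less the last earlier dispensing date.
- **sMTS:** C is the "Number of missed doses from kits dispensed during the last drug dispensing visit before 01 March 2020", restricted to kits with a scheduled return after that date. It is multiplied by the elapsed days divided by 30: "last drug dispensing date prior to 01 March 2020})/30". There is no cap, no use of the actual interval and no rule for early stopping.

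In both arms the result is rounded to the nearest integer, and the later period is found by subtraction: "Number of doses delivered on or after 01 March 2020 = Number of doses delivered during whole study" less the count before. The reason given for two formulas is that "The number of doses provided to a subject is different at each visit between the abaloparatide-SC group and abaloparatide-sMTS group". The results are summarised by treatment group for the Safety, mITT and PP populations.

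**The concern.** Both formulas do the same job: they spread diary-recorded missed doses over calendar time. The quantity supplied appears in neither, so the stated reason does not explain why one arm uses the real interval and the other a constant. The 20-patch kit size enters only the separate calculation from returned patches.

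The constant is right only when the spanning interval is 30 days. Protocol 6.2 allows each visit a window of 4 days either side, and the SAP expects missed and out-of-window visits during the pandemic (categories in SAP 4.1). The interval that spans 1 March 2020 is therefore one that may well depart from 30 days. Because the later count is obtained by subtraction, an error in the first period reappears with opposite sign in the second. At stake is whether a between-arm difference in the before/after table reflects conduct or the formula.

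**Working it through.** The documents give no numerical result for this split, so there is no figure to reproduce. The formulas come from SAP 4.3.1. The dates and missed-dose counts below are assumptions, identical in both arms, with no other missed doses (B = 0).

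**General form.** Let d be the days from the last earlier dispensing to 1 March, and I the actual interval (or time to last dose). Missed doses placed before the date are C × d/I for SC and C × d/30 for sMTS. The gap before rounding is C × d × (1/30 − 1/I). It is zero if C = 0 or I = 30. For I above 30, sMTS places more missed doses before the date than SC does; for I below 30, fewer.

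**On schedule.** First dose and dispensing 10 February, next dispensing 11 March (I = 30), C = 10, so A = 20 and d = 20. Both rules give 20 − 6.67 = 13.33, rounded to 13; 13/20 = 65.0%.

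**At the edges of the visit window, otherwise the same data.**
- I = 26: SC 12/20 = 60.0%, sMTS 13/20 = 65.0%.
- I = 34: SC 14/20 = 70.0%, sMTS 13/20 = 65.0%.

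**Delayed visit within labelled supply.** First dose 11 January, so A = 50. Dispensed 10 February (d = 20), next dispensing 21 March (I = 40), C = 10, 360 days in total. That is 350 doses delivered and 310 days from 1 March. The interval uses 40 − 10 = 30 doses, which is one pen (Protocol 5.1.2).
- SC: 10 × 20/40 = 5. Before 45/50 = 90.0%; after (350 − 45)/310 = 305/310 = 98.4%.
- sMTS: 10 × 20/30 = 6.67, so 43.33, rounded to 43. Before 43/50 = 86.0%; after 307/310 = 99.0%.

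**Early stop.** Dispensed 25 February (d = 5), last dose 2 March (I = 6), C = 4. Two days fall on or after 1 March. Total delivered is A + 2 − 4 = A − 2.
- SC: 4 × 5/6 = 3.33; before A − 3; after (A − 2) − (A − 3) = 1 of 2.
- sMTS: 4 × 5/30 = 0.67; before A − 1; after (A − 2) − (A − 1) = −1 of 2, or −50%.

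A second case has a longer history: first dose 17 November 2019 (A = 105), dispensed 15 February (d = 15), last dose 5 March (I = 19), C = 12, with 98 delivered over 110 days.
- SC: 12 × 15/19 = 9.47; before 96; after 2/5 = 40%.
- sMTS: 12 × 15/30 = 6; before 99; after −1/5 = −20%.

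**Grid of early stops.** This covered 5,936 combinations, with scheduled return 30 days after dispensing and at most 14 missed doses. The sMTS rule gave an impossible count in 626 (10.5%) and the SC rule in none. These are combinations, not expected frequencies.

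**Share above 1.** If the scheduled return is dispensing plus 30 days, a kit enters C only when d is below 30, so the share stays below 1. It exceeds 1 only if the scheduled return can be later. For example, dispensing on Day 26 (4 days early), return scheduled for Day 60 and 1 March on Day 59 give (59 − 26)/30 = 1.10.

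**The case against.** The strongest reply is that the protocol's month is 30 days, so on schedule the formulas agree, and close to schedule the gap is usually trivial. That stands. With C = 2, d = 20 and I = 34, the gap is 2 × 20 × (1/30 − 1/34) = 0.16 of a dose. The 5-point gaps above needed 10 missed doses in one period and only 20 days of earlier exposure.

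A reader might stretch the delayed visit to 60 days with 12 missed doses, which would give 92.0% against 84.0% before the date. That implies 60 − 12 = 48 doses from one dispensing: more than a 30-dose pen, more than two 20-patch kits, and more than the plunger figures in SAP 4.3.1 allow (45.5/1.08, about 42). The stated supply figures do not support that contrast.

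A reader might also infer that the missing cap matters routinely. It matters only under one reading of *scheduled return date*, which the SAP leaves undefined. At a share of 1.10 the excess is 0.1 × C, under half a dose unless at least 5 were missed. The SC cap never binds here either, since the next dispensing or last dose falls on or after 1 March.

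Nor do the documents show a systematic bias between arms. Delays and early stops push in opposite directions, and the number of subjects affected is not given. Pandemic effects on dosing are also captured through the COVID-19 Impact Log and the summary of missed and interrupted doses.

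None of this removes the negative counts after an early stop, which need no special reading of the text.

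**Conclusion.** The inconsistency is real and minor. When doses were missed in the spanning period and the actual interval or time to last dose is not 30 days, the same data can give different compliance by arm. In the 40-day illustration the gap is two doses: 4 percentage points before the date and about 0.6 after it (2/310). For a subject who stops soon after 1 March, the sMTS rule as written can return a negative count.

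These sizes rest on assumed dates and missed-dose counts for single subjects and do not estimate a group-level effect. The consequence is confined to the descriptive before/after 1 March 2020 compliance summaries. A reader might suppose that the per-protocol set or the non-inferiority result is touched. Neither is: the 80% exclusion rule uses the two compliance calculations for the study as a whole, and the primary MMRM does not use this split.

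**What to change.** Use one rule in both arms of SAP 4.3.1. There are two options:

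- Apply the SC share, min{1, D/E}, to sMTS, with D in days and the SC definition of E, including the last-dose rule. Identical data then give identical results, the −50% above becomes 1 of 2 doses, and the impossible values in the grid fall to none.
- If the diary data hold the date of each missed dose, count missed doses by date in both arms. No proration is then needed.

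In either case, define *scheduled return date*, because it decides which missed doses enter B and which enter C.

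The cost is a small change of wording and code. The first option has a limitation: it still assumes that missed doses are spread evenly over the interval. If a subject used supply daily until it ran out and then waited for a late visit, D/E would place some later misses before 1 March. It makes the arms consistent but not necessarily accurate, so counting by date is preferable where the data allow it.
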